#### **Analysis of other continuous secondary endpoints**

For each of the other continuous secondary endpoint, the following by visit summary tables will be provided.

- Summary table at each scheduled visit up to Week 24 [REDACTED]  
[REDACTED]  
[REDACTED]  
[REDACTED]  
[REDACTED] Mean difference with 95% CI and p-value will be provided.
- Summary table at each scheduled visit up to Week 24 [REDACTED]  
[REDACTED]
- Summary table at each scheduled visits from Week 24 onwards, [REDACTED]  
[REDACTED]  
[REDACTED]  
[REDACTED]  
[REDACTED] The change value (or percent change value) is calculated using Week 0 baseline value. Summary is presented using Week 24 re-randomization treatment arms.
- Summary table at each scheduled visits from baseline to Week 52, [REDACTED]  
[REDACTED]  
[REDACTED]  
[REDACTED]  
[REDACTED] The change value (or percent change value) is calculated using Week 0 baseline value. Summary is presented using Week 24 re-randomization treatment arms.
- Summary table at each scheduled visit from Week 24 onwards, [REDACTED]  
[REDACTED]  
[REDACTED] The change value (or percent change value) is calculated using Week 0 baseline value. Summary is presented using Week 24 re-randomization treatment arms.
- Summary table at each scheduled visit from baseline up to Week 52, [REDACTED]  
[REDACTED]  
[REDACTED] The change value (or percent change value) is calculated using Week 0 baseline value. Summary is presented using Week 24 re-randomization treatment arms.

[Redacted]

For each of the other continuous secondary endpoint, the following line plots will be provided:

- Line plot will be provided including scheduled visits up to Week 24 using the LSMEAN estimation from the above by visit summary table.
- Line plot will be provided including scheduled visits from Week 24 up to Week 52 among patients in Part 2 using the mean change (or percent change) estimation from the above by visit summary table [Redacted]. The change value (or percent change value) is calculated using Week 0 baseline value. The line plot will be presented using Week 24 re-randomization treatment arms.
- Line plot will be provided including scheduled visits from baseline up to Week 52 among patients in Part 2 using the mean change (or percent change) estimation from the above by visit summary table [Redacted]. The change value (or percent change value) is calculated using Week 0 baseline value. The line plot will be presented using Week 24 re-randomization treatment arms .

**Analysis of other categorical secondary endpoints**

For each of the other categorical secondary endpoints, the following by visit summary tables will be provided.

- Summary table at each scheduled visit up to Week 24 [Redacted]  
[Redacted]  
[Redacted] Proportion difference with 95% CI and p-value will be provided.
- Summary table at each scheduled visit up to Week 24 [Redacted]  
[Redacted]
- Summary table at each scheduled visits from Week 24 onwards, [Redacted]  
[Redacted]

[REDACTED]  
[REDACTED] Summary is presented using Week 24 re-randomization treatment arms.

- Summary table at each scheduled visits from Week 24 onwards, [REDACTED]  
[REDACTED]  
[REDACTED]  
[REDACTED]

[REDACTED] Summary is presented using Week 24 re-randomization treatment arms.

- Summary table at each scheduled visits from baseline to Week 52, [REDACTED]  
[REDACTED]  
[REDACTED]

[REDACTED]. Summary is presented using Week 24 re-randomization treatment arms.

- Summary table at each scheduled visit from Week 24 onwards, [REDACTED]  
[REDACTED]

[REDACTED] Summary is presented using Week 24 re-randomization treatment arms.

- Summary table at each scheduled visit from baseline to Week 52, [REDACTED]  
[REDACTED]

[REDACTED] Summary is presented using Week 24 re-randomization treatment arms.

- A summary of percentage of patients with at least a 75% reduction from baseline in EASI (EASI 75) and percentage of patients with response of IGA 0 or 1 will be presented from Week 24 to Week 52 by Part 1 rescue medications and/or prohibited medications/procedures impacting efficacy use (yes or no).

For each of the other categorical secondary endpoint, the following line plots will be provided:

- Bar plot will be provided including scheduled visits up to Week 24 [REDACTED]  
[REDACTED]

- Bar plot will be provided including scheduled visits from Week 24 onwards, [REDACTED]  
[REDACTED] It will be presented using Week 24 re-randomization treatment arms.

- Bar plot will be provided including scheduled visits from Week 24 onwards, [REDACTED]  
[REDACTED]  
[REDACTED]

[REDACTED] It will be presented using Week 24 re-randomization treatment arms.

- Bar plot will be provided including scheduled visits from baseline to Week 52 for patients in Part 2, [REDACTED]

[Redacted]  
[Redacted] It will be presented using Week 24 re-randomization treatment arms

**Analysis of time to event other secondary endpoints**

Time to loss of EASI 75, IGA 0/1, and EASI 50 in patients who re-randomized to Part 2 will be summarized. Kaplan-Meier curves will be presented by the re-randomized treatment groups. When with reasonable number of patients entering each treatment arm during Part 2, two-sided log-rank test (based on stratification factors) and the corresponding p-value might be provided to compare the active treatment group vs corresponding withdrawal placebo arm. Off study treatment data up to Week 52 will be included in the analysis (treatment policy) for patients who discontinued study treatment before Week 52. [Redacted]

[Redacted]  
[Redacted] If applicable, the Kaplan-Meier estimates for the median time, the first and third quartiles might be presented along with approximate 95% CI's.

**8.4 Exploratory Efficacy Endpoints**

- [Redacted]
- [Redacted]
  - [Redacted]
  - [Redacted]
  - [Redacted]
  - [Redacted]
  - [Redacted]

The detailed information will be provided in a separate SAP document for the Biomarker Analysis.

**9. Safety Analysis**

Safety will be assessed through the collection and evaluation of AEs, including TEAEs and SAEs, AESIs, clinical laboratory assessments, physical examinations, vital sign measurements, and ECGs. All the analysis will be based on SAF1 & SAF2 for Part 1 and Part 2, respectively.

**9.1 Adverse Events**

The ICH E6(R2) Good Clinical Practice Guideline defines an AE as any untoward medical occurrence in a patient or clinical investigation patient administered a pharmaceutical product, which does not necessarily have to have a causal relationship with this treatment. An AE can, therefore, be any unfavourable and unintended sign (including an abnormal laboratory finding), symptom or disease temporally associated with the use of a medicinal (investigational) product, whether or not considered related to the medicinal (investigational) product.

**Pre-treatment AE, treatment-emergent AE, post-treatment AE definition**

The pre-treatment period is defined as the period up to first IMP administration.

The treatment-emergent (TE) period is defined as the period from the first IMP administration to the last IMP administration + 140 days.

The post-treatment period is defined as the period from the end of the treatment-emergent period onwards.

The AEs will be analyzed in the following 3 categories:

Pre-treatment AEs: AEs that developed, worsened, or became serious during the pre-treatment period.

TEAEs: AEs that developed, worsened or became serious during the treatment-emergent period;

Post-treatment AEs: AEs that developed, worsened, or became serious during the post-treatment period.

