In those patients who achieve ≥ EASI 75 or who attain IGA 0/1 at Day 169 (Week 24), a randomisation will occur pre-dose at Day 169 (Week 24) and patients will enter the second study period. This will occur irrespective of whichever dose group the patient was randomised to at Baseline including Placebo. Patients will be randomised in a 3:1 manner to be withdrawn from therapy or to continue their pre-Week 24 dose/interval. To maintain the blind, those patients randomised to the Withdrawal arm will receive Placebo Q4W. Those patients who are re-randomised at Day 169 (Week 24) who lose their clinical response will be offered the opportunity to be retreated with KY1005 in the LTE study. Loss of clinical response is defined as the first instance of <EASI 50 during the second study period and where rescue therapy is no longer permitted as per Section 5.3.4. If loss of clinical response from Day 197 (Week 28) occurs, Investigators will be able to choose to discontinue the patient from KY1005-CT05

At Day 365 (Week 52), patients who have completed the post-Week 24 period and have not experienced loss of clinical response will have an additional 112 days' safety follow-up up to Day 477 (Week 68) and then be discharged from the study. The last dose will be given no later than Day 337 (Week 48) and as such safety follow-up will be 140 days following last dose of IMP. If during safety follow-up or after the end of study this cohort of patient's experience worsening of their AD, and in the investigator's opinion re-treatment with KY1005 is considered appropriate, they may be considered for enrolment in the LTE (subject to meeting inclusion/exclusion criteria).

The overall study design is presented in Figure 3-1.

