ADAs=anti-drug antibodies; ADCT=atopic dermatitis control tool; AEs=adverse events; BSA=body surface area; DLQI=Dermatology Quality of Life Index; EASI=Eczema Area and Severity Index; ECG=electrocardiogram; FBC=full blood count; IgE=immunoglobulin E; IMP=Investigational Medicinal Product; NRS=Numerical Rating Scale; POEM=Patient Oriented Eczema Measure; PK=pharmacokinetics; PRO=patient reported outcome; SAE=serious adverse event; SCORAD=SCORing of Atopic Dermatitis; IGA= Investigator Global Assessment; HADS= Hospital Anxiety and Depression Scale.

- # Early Termination could be done by the Sponsor or the Investigator (see Section 3.4, Section 3.5 and Section 9).
- a On IMP administration days in this time period, all assessments, including taking blood samples, will be performed pre-injection unless stated otherwise.
- b On IMP administration days in this time period, vital signs will be measured pre-injection and 30 minutes post- injection. The tolerance on vital signs after dosing is ±5minutes.
- d NRS (pruritus) will be recorded daily, ideally in the morning, based on the previous 24 hours with worst (maximum) itch intensity recorded.
- f A telephone visit is defined as a videoconference, video call or telephone call.
- g Where possible, the PRO assessments completed at the study site are to be completed by patients prior to the completion of other study assessments and the administration of IMP.
- If urine pregnancy test is positive, a serum control must be done before IMP administration.

The ICF from the DRI/Phase2b/parent study will not be valid as LTE informed consent. In order for patients to roll over to the LTE a specific LTE ICF will need to be applied, agreed upon and signed at the LTE study, as the LTE is a separated protocol.

Table 6-4: Schedule of Assessments - SafetyFollow-up

Visit	29 ^a	30 ^a	31ª	32ª	
Visit days	393	421	449	477	F/D#
Visit weeks	56 ^d	60 ^d	64 ^d	68 ^d	ET#
Visit window (days)	±7	±7	±7	±7	
Description	Clinic	Telephone ^b	Clinic	Clinic	Clinic
Concomitant medications - including emollients	X	X	X	X	X
AEs (including SAEs)	÷				X
Physical examination			X	X	X
Vital signs	X		X	X	X
12-lead ECG	X		X	X	X
Safety tests (FBC, non-fasting biochemistry, electrolytes, urinalysis)	X		X	X	X
Pregnancy test – females only (urine) ^c	X		X	X	X
Blood samples for serum concentrations of ADAs					

ADA=anti-drug antibody; AEs=adverse events; ECG=electrocardiogram; FBC=full blood count; SAE=serious adverse event.

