#### Patient's ADA status

- Patients with **pre-existing ADAs** correspond to patients with ADAs present in samples drawn before first administration of intervention. Patients with missing ADA sample at baseline will be considered as without pre-existing ADA.
- Patients with **treatment-emergent ADA** correspond to patients with at least one treatment-induced/boostered ADA.
- Patients with **treatment-induced ADAs** correspond to patients with ADAs that developed during the treatment-emergent (TE) period and without pre-existing ADA (including patients without pre-treatment samples).
- Patients with **treatment-boostered ADAs** correspond to patients with pre-existing ADAs that are boosted during the TE period to a significant higher titer than the baseline. A 2-fold serial dilution schema is used during titration, so at least a 4-fold increase will be considered as significant.
- Patients with **unclassified ADA** correspond to patients with pre-existing ADAs that cannot be classified as treatment-boostered ADA because of missing titer(s) (ie, a positive ADA sample during the TE period in a patient with pre-existing ADA but with missing titer at this sample or at baseline).

- Patients **without treatment-emergent ADA** correspond to patients without treatment-induced/boosted ADA and without any inconclusive sample nor unclassified ADA during the TE period.
- Patients **with inconclusive ADA** are defined as patients which cannot irrefutably be classified as with or without treatment-emergent ADA.

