### **Kinetics of ADA response**

Kinetics of ADA response will be derived for patients with treatment-induced/boosted ADA considering ADA samples collected during the TE period and post-treatment period.

- Time to onset of ADA response is defined as the time period between the first IMP administration and the first treatment-induced/boosted ADA.
- Duration of ADA response is defined as the time between the first treatment-induced/boosted ADA and the last treatment-induced/boosted ADA, irrespective of negative samples or positive samples not reaching the boosted threshold in-between. ADA duration will be summarized only for patients with persistent ADA response.
- Persistent ADA response is defined by treatment-induced/boosted ADA with a duration of ADA response of at least 16 weeks.
- Transient ADA response is defined by treatment-induced/boosted ADA with a duration of ADA response of less than 16 weeks and the last sample of the TE period is not treatment-induced/boosted.
- Indeterminate ADA response is defined by treatment-induced/boosted ADA that are neither persistent nor transient.

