### **ADA response variable:**

- ADA incidence is defined as the proportion of patients found to have seroconverted (treatment-induced ADAs) or boosted their pre-existing ADA response (treatment-boosted ADAs) at any time point during the TE period.

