**Table 14 Analyses window definition for Safety Parameters**

Scheduled visit baseline /post baseline	Targeted study day	Analysis window in study days	Safety Parameters
Visit 1	0	< 1	PE, VS, LAB, ECG,
Week 0 (Visit 2)	1	1	PE, VS, LAB, ECG,
Week 2 (Visit 4)	15	2 to 22	PE
Week 4 (Visit 6)	29	23 to 43	PE, VS, LAB, ECG,
Week 8 (Visit 7)	57	44 to 71	PE, VS, LAB, ECG,
Week 12 (Visit 8)	85	72 to 99	PE, VS, LAB, ECG,
Week 16 (Visit 9)	113	100 to 127	PE, VS, LAB, ECG,
Week 20 (Visit 11)	141	128 to 155	PE, VS, LAB,
Week 24 (Visit 15)	169	156 to 183	PE, VS, LAB, ECG,
Week 28 (Visit 17)	197	184 to 211	PE, VS, LAB,
Week 32 (Visit 19)	225	212 to 239	PE, VS, LAB, ECG,
Week 36 (Visit 21)	253	240 to 267	PE, VS, LAB,
Week 40 (Visit 22)	281	268 to 295	PE, VS, LAB, ECG,

Week 44 (Visit 24)	309	296 to 323	PE, VS, LAB,
Week 48 (Visit 26)	337	324 to 351	PE, VS, LAB, ECG,
Week 52 (Visit 28)	365	352 to 379	PE, VS, LAB, ECG,
Week 56 (Visit 29)	393	380 to 407	VS, LAB, ECG
Week 60 (Visit 30)	421	408 to 435	PE, VS, LAB, ECG
Week 64 (Visit 31)	449	436 to 463	PE, VS, LAB, ECG
Week 68 (Visit 32)	477	> 463	PE, VS, LAB, ECG

 
Adverse events, Concomitant medications are collected from screening and throughout the study.
 
Study days are calculated considering Day 1 as the day of first administration of intervention (or the day of randomization for patient not exposed).
 
 
updated
			

Table 15 Analyses window definition for PK Parameters

Scheduled visit baseline /post baseline	Targeted study day	Analysis window in study days	PK Parameters
Week 0 (Visit 2)	1	1	PK, ADAs, total IgE/soluble protein
Week 1 (Visit 3)	8	5 to 11	PK
Week 2 (Visit 4)	15	12 to 22	PK, ADAs
Week 4 (Visit 6)	29	23 to 43	PK, ADAs, total IgE/soluble protein
Week 8 (Visit 7)	57	44 to 71	PK
Week 12 (Visit 8)	85	72 to 99	PK
Week 16 (Visit 9)	113	100 to 117	PK, ADAs, total IgE/soluble protein
Week 17 (Visit 10)	120	118 to 131	PK
Week 20 (Visit 11)	141	132 to 155	PK
Week 24 (Visit 15)	169	156 to 173	PK, ADAs, total IgE/soluble protein
Week 25 (Visit 16)	176	174 to 187	PK
Week 28 (Visit 17)	197	188 to 211	PK
Week 32 (Visit 19)	225	212 to 239	PK

Week 36 (Visit 21)	253	240 to 267	PK, ADAs, total IgE/soluble protein
Week 40 (Visit 22)	281	268 to 295	PK
Week 44 (Visit 24)	309	296 to 323	PK
Week 48 (Visit 26)	337	324 to 351	PK, ADAs
Week 52 (Visit 28)	365	352 to 421	PK, ADAs, total IgE/soluble protein
Week 68 (Visit 32)	477	> 421	ADAs

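### The treatment-emergent period used for ADA ends on the target day of the last ADA sample with no visit tolerance, so some in-window Week 68 samples cannot count towards ADA incidence

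*SAP*

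**What the plan says.** SAP section 9.1 gives a single treatment-emergent (TE) period: "The treatment-emergent (TE) period is defined as the period from the first IMP administration to the last IMP administration + 140 days". It then says: "The post-treatment period is defined as the period from the end of the treatment-emergent period onwards". No tolerance for visit timing is added.

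SAP section 10.3 has no ADA-specific period and relies on the same term:

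- Treatment-induced patients are those with "ADAs that developed during the treatment-emergent (TE) period and without pre-existing ADA". Boosting must also occur in the TE period.
- ADA incidence counts patients who seroconvert or boost "at any time point during the TE period".
- A transient response needs a duration under 16 weeks and that "the last sample of the TE period is not treatment-induced/boosted".
- Post-treatment samples enter the kinetics, which are derived only for patients already classed as treatment-induced or boosted.

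On timing, Protocol section 3.1 places the last dose no later than Day 337, so that "safety follow-up will be 140 days following last dose of IMP". In Protocol section 6.1, "Table 6-4: Schedule of Assessments - SafetyFollow-up" sets the final visit at Day 477 with a window of ±7 days. SAP Table 15 lists ADA at Week 68 and maps any sample after Day 421 to that visit, with no upper limit.

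**The concern.** The cut-off and the target day of the last ADA sample coincide. Take two compliant patients, both dosed on Day 337 and both first positive at Week 68. If one attends on Day 477 and the other on Day 478, the first counts in ADA incidence and the second does not. The kinetics do not recover the second patient, because they require a prior classification as induced or boosted.

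The transient rule has the same edge. Suppose a patient is first positive at Week 52 and negative at Week 68. With the Week 68 sample on Day 477, the last TE sample is negative and the response is transient. With it on Day 478, the last TE sample is the positive one from Week 52 and the response becomes indeterminate.

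The immunogenicity of KY1005 is a named secondary endpoint. Its incidence and classification should not turn on which permitted day a patient attends.

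**Working it through.** **Inputs**

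- TE period end: last IMP + 140 days (SAP 9.1).
- Last planned dose: Day 337 (Protocol 3.1), visit window ±3 days, so Days 334 to 340 (Protocol Table 6-3).
- Last ADA sample: Week 68, Day 477 (SAP Table 15), visit window ±7 days, so Days 470 to 484, which is 15 days (Protocol Table 6-4).
- Actual distribution of visit days: not in the documents. Any share of samples is therefore an assumption.

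I treat the day that is exactly 140 days after the last dose as inside the TE period.

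**The plan's own sum.** 337 + 140 = 477. This reproduces the Day 477 that the protocol synopsis gives as the end of follow-up.

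**Permitted days after the cut-off.** With the dose on Day 337, Days 478 to 484 fall outside: 7 of 15 = 46.7%. When the dose day moves within its window:

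| Dose day | TE end | Week 68 days outside |
|---|---|---|
| 334 | 474 | 10/15 (66.7%) |
| 335 | 475 | 9/15 (60.0%) |
| 336 | 476 | 8/15 (53.3%) |
| 337 | 477 | 7/15 (46.7%) |
| 338 | 478 | 6/15 (40.0%) |
| 339 | 479 | 5/15 (33.3%) |
| 340 | 480 | 4/15 (26.7%) |

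The sum is 10 + 9 + 8 + 7 + 6 + 5 + 4 = 49 of 7 × 15 = 105 day combinations, again 46.7%. If the protocol's limit of Day 337 for the last dose is read strictly, only the first four rows apply and the range is 7/15 to 10/15.

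**Sensitivity to visit timing (dose on Day 337)**

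- Triangular around the target: 43.8%.
- Normal centred on the target, SD 1, 2, 3 or 4 days: 30%, 40%, 43% or 45%.
- Normal with SD 2 days: 10% if visits average 2 days early, 78% if they average 2 days late.

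**Candidate extensions**

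- Last IMP + 147 days: the TE end is 484 plus the dose offset. Doses 3, 2 and 1 days early leave 3, 2 and 1 days outside, so 6/105 = 5.7%.
- Last IMP + 150 days: the earliest TE end is 334 + 150 = 484, so 0/105.

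**The case against.** The strongest reply is that this is an edge case in a descriptive summary. Incidence is met by a qualifying result at any TE time point, and Table 15 also schedules ADA at Weeks 2, 4, 16, 24, 36, 48 and 52. Patients who enter the LTE do not have the Week 68 visit. Sample status is described without any stated TE restriction, so a late positive is still reported. No test or decision rule uses ADA, and the 140 days match the protocol's TEAE definition. All of this stands, and it limits the size of the effect. It does not remove the misclassification.

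A reader might infer three stronger things that the documents do not support:

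- *That about half of Week 68 samples are lost, or that incidence is understated by a similar share.* The documents give 7 of 15 permitted days. A share of samples needs an assumed spread of visits, and a share of samples is not a share of patients reclassified.
- *That the sample at risk is always the one taken 140 days after active drug.* IMP includes placebo. Patients re-randomised to withdrawal (3:1) have their last KY1005 dose planned for Day 141, so Day 477 is 477 − 141 = 336 days later. The 140-day interval from active drug fits only those who continued KY1005.
- *That the 16-week persistence rule needs the same repair.* It is a stated definition in elapsed time, and any such limit has an edge. Counting nominal visits instead would class in-window samples on Days 368 and 470, only 102 days apart, as persistent.

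**Conclusion.** The point holds as a drafting defect in SAP 10.3. Read as written, the SAP places 7 of the 15 permitted Week 68 sampling days outside the TE period when the last dose is on Day 337, and 4 to 10 of 15 across the ±3-day dose window. The 47% figure applies to samples only if visits are evenly spread.

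The error in incidence runs one way: first positives can be lost and none gained. The size of the bias cannot be computed from the documents. It is probably small, because it needs a patient who stays out of the LTE, is followed to Week 68, and has a first induced or boosted result there after the cut-off. The shift from transient to indeterminate likewise needs the Week 68 sample to be late and negative, with the preceding TE sample still positive.

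The conclusion assumes that section 10.3 means the TE period of section 9.1. The SAP text gives no other.

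**What to change.** In SAP 10.3, state that for ADA classification the TE period includes the scheduled Week 68 sample by nominal visit. Alternatively, extend the ADA period to last IMP + 150 days, which covers both the ±3-day dose window and the ±7-day visit window; 147 days does not. Use the same period for ADA incidence and for the last-sample condition in the transient rule. Leave the adverse-event window at 140 days and the 16-week persistence definition as it is.

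The two options differ for patients who stop dosing early but are still sampled at Week 68. After a last dose on Day 309, for example, Day 477 is 168 days later: the nominal-visit rule counts that sample and the 150-day rule does not. The SAP should say which is intended.

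The cost is one or two sentences and a small programming change, with no new samples. The drawback is that the ADA and adverse-event periods then differ, by a few days for patients dosed to Week 48, which a table footnote can explain.
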